##### 6.1.1.2. Sensitivity/Supplementary Analyses

A sensitivity analysis will be performed on the complete analysis set, as defined in Section 4. The analysis will mirror the main analysis as laid out in Section 6.1.1.1, but will use Estimand 1b (as described in Section 2.2.3).

Additionally, a supplementary analysis will be performed on the censored analysis set, as defined in Section 4. The summaries and analysis will mirror the main analysis as laid out in Section 6.1.1.1, but will be restricted to participants with a KCCQ-23 CSS score at baseline < 75.

### 6.2. Secondary Endpoint(s)

The efficacy analyses will be performed on the censored analysis sets, as defined in Section 4, and using efficacy approaches 1 and 3, as described in Section 5.2.

**6.2.1. Change from baseline in KCCQ-23 CSS, OSS, TSS, and physical limitation at Week 22 (Cohorts A and C)**

Summaries and analyses will use efficacy approach 3 for all endpoints, as described in Section 5.2 and efficacy approach 1 for all endpoints other than CSS (which has already been detailed in Section 6.1).

KCCQ-23 CSS, OSS, TSS and physical limitation will each be summarized and analyzed across all timepoints, in a similar manner to the main analysis of the primary endpoint, as outlined in Section 6.1.1.1. This analysis will estimate the treatment effect related to Estimand 2 (as described in Section 2.2.4). Note that for efficacy approach 3, cohort will be included as a term in the statistical model.

For KCCQ-23 CSS score, a supplementary analysis will also be performed. The summaries and analysis will mirror that described above, but will be restricted to participants with a KCCQ-23 CSS score at baseline < 75.

**6.2.2. Response as defined by a  $\geq 5$ -point increase from baseline in KCCQ-23 CSS, OSS, TSS, and physical limitation at Week 22 (Cohorts A and C)**

Summaries and analyses will use efficacy approaches 1 and 3 for all endpoints, as described in Section 5.2.

Responses as defined by a  $\geq 5$ -point increase in KCCQ-23 CSS, OSS, TSS, and physical limitation score will be summarized descriptively by treatment group and timepoint, as described in Section 5.2.2, with no imputation for missing data. Tables will include all post-baseline timepoints. Plots of the percentages over time will also be produced, with all treatments on the same plot for each score.

The percentage of responses (and 90% CIs) at Week 22 will also be reported by treatment after multiple imputation for missing values as per Section 5.3.4. These responses *will also be analyzed separately using Estimand 3 and a logistic regression model* with multiple imputation (as described in Section 5.2.4), where missing values will be imputed using multiple imputation as per Section 5.3.4. *The logistic regression model will be fitted to the data at Week 22 only.* Note that for efficacy approach 3, cohort will be included as a term in the statistical model.

For KCCQ-23 CSS score, a supplementary analysis will also be performed. The summaries and analysis will mirror that described above, but will be restricted to participants with a KCCQ-23 CSS score at baseline < 75.

**6.2.3. Change from baseline in 6MWD at Week 22 (Cohorts A and C)**

Summaries and analyses will use efficacy approaches 1 and 3, as described in Section 5.2.

6MWD will be summarized and analyzed across all timepoints, in a similar manner to the main analysis of the primary endpoint, as outlined in Section 6.1.1.1. This analysis will

estimate the treatment effect related to Estimand 4 (as described in Section 2.2.4). Note that for efficacy approach 3, cohort will be included as a term in the statistical model.

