4. STUDY DESIGN

4.1. Overall Design

This is a Phase 2, parallel-group, randomized, double-blind, placebo-controlled study to evaluate the effect of ponsegromab on HRQL, physical activity, and circulating biomarkers in adult participants with HF and elevated circulating GDF-15.

For the Main Cohort (Cohort A), Cohort C, and Cohort D, following the 56-day screening period to confirm eligibility, the study will include a 22-week treatment period (from Day 1 to Week 20, and Week 22 for primary endpoint collection), and a 10-week follow-up period for a total study duration of 32 weeks not including the screening period.

Approximately 416 participants will be enrolled into the Main Cohort (Cohort A) and randomized to one of 3 doses of ponsegromab (100 mg [n=18], 200 mg [n=18], or 300 mg [n=190]) or to matched placebo (n=190). Approximately 195 additional participants may be enrolled into optional Cohort C and randomized in a 2:1 ratio to either 100 mg ponsegromab (n~130) or to matched placebo (n~65). The participants in optional Cohort C will allow for a more comprehensive evaluation of the safety and efficacy of the ponsegromab 100 mg dose level compared to placebo. For each of these cohorts, blinded study drug will be administered SC Q4W for a total of 6 doses during the 22-week treatment period.

Participant randomization will be stratified based on CCI

CCI

KCCQ-23 CSS: <45 or ≥45.

The primary endpoint for the study is the change from baseline at Week 22 in KCCQ-23 CSS, an HRQL PRO instrument.

Approximately 100 participants (maximum of approximately 150) who meet all eligibility criteria for Cohorts A and C, except the requirement for serum GDF-15 concentration CCI pg/mL, may be enrolled into the optional Cohort D and randomized in a 1:1 ratio to either 300 mg ponsegromab (n~50) or to matched placebo (n~50), administered SC Q4W for a total

of 6 doses during the 22-week treatment period. Participant randomization in Cohort D will be stratified by KCCQ-23 CSS: <45 or ≥ 45 . The purpose of this optional cohort is for a supportive assessment of efficacy and safety endpoints across the spectrum of GDF-15 concentrations in participants with HF.

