6.3. Assignment to Study Intervention

Allocation of participants to treatment groups in Main Cohort (Cohort A), Cohort C and Cohort D will proceed through the use of an IRT system. The site personnel (study coordinator or specified designee) will be required to enter or select information including but not limited to the user's ID and password, the protocol number, and the participant number. Randomization is stratified based on KCCQ-23 CSS score (Main Cohort [Cohort A], Cohort C and Cohort D) and GDF-15 concentrations (Main Cohort [Cohort A] and Cohort C only) from SV1 assessments; these data points will be required to be entered in the IRT system to ensure appropriate randomization allocations.

The site personnel will then be provided with a randomization number corresponding to the assigned treatment group, and DU or container number(s) when study intervention is being supplied via the IRT system. The IRT system will provide a confirmation report containing the participant number, randomization number, and DU or container number assigned. The confirmation report must be stored in the site's files.

Study intervention will be administered at the study visits summarized in the [SoA](#).

The study-specific IRT reference manual and IPM will provide the contact information and further details on the use of the IRT system.

Open-label, PK cohort (Cohort B): This is an open-label cohort; however, the specific treatment assignment (ie, 100 mg, 200 mg, or 300 mg open-label dose arm) will be assigned using the IRT system. Randomization for this cohort is not stratified.

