**Figure 1. Study Design**

### 3. ENDPOINTS AND BASELINE VARIABLES: DEFINITIONS AND CONVENTIONS

For all safety endpoints, unless otherwise stated, baseline is defined as the last pre-dose measurement. For all efficacy endpoints, unless otherwise stated, baseline is defined as the last measurement on study day 1.

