#### **5.2.6. Logistic Regression without multiple imputation**

The logistic regression model will include treatment as a fixed term in the model. Additional terms may be fitted in the model (eg, cohort, baseline LVEF, log GDF-15 concentration from SV1, baseline log NT-proBNP), as appropriate. Missing values (e.g. due to censoring) will not be imputed. Odds (and 90% CIs) and odds ratios versus placebo (and 90% CIs [and p-values, for selected endpoints]) will be provided. No adjustments will be made for multiplicity.

Standard SAS output will be provided to support the statistical summary table for the analysis model, but will not be included in the CSR.

Example SAS code is provided in Appendix 4.

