#### **5.2.8. Cox Proportional Hazards Model**

The Cox proportional hazards model will include treatment as a fixed term in the model. Additional terms may be fitted in the model (eg, cohort, baseline LVEF, log GDF-15 concentration from SV1, baseline log NT-proBNP, baseline KCCQ-23 CSS), as appropriate. Hazard ratios versus placebo (and 90% CIs) will be provided. No adjustments will be made for multiplicity.

Standard SAS output will be provided to support the statistical summary table for the analysis model.

Example SAS code and further details of the statistical methodology is provided in Appendix 4.

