##### 6.1.1.1. Main Analysis

This analysis will be performed on the censored analysis set, as defined in Section 4.

Absolute values and changes from baseline in the KCCQ-23 CSS score will be summarized descriptively by treatment group and timepoint, as described in Section 5.2.1. Tables will include baseline and all post-baseline timepoints.

*Change from baseline in KCCQ-23 CSS at Week 22 will be analyzed using Estimand 1 and an MMRM model, as described in Section 5.2.3. The MMRM model will be fitted to the change from baseline at all post-treatment timepoints up to Week 22 using the Censored analysis set (as defined in Section 4) from Cohort A participants only. Additional terms for baseline LVEF, log CCI GDF-15 concentrations from SV1 and baseline log NT-proBNP will be fitted in the model.*

Additional plots of LS means and differences (including 90% CIs for both), for Week 22 only, will be produced over treatment (for the primary endpoint only).

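### The models for 6MWD, PROMIS Fatigue, body weight, activity and biomarkers leave out the KCCQ-23 CSS stratification factor, so their standard errors are likely to be mildly conservative

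*SAP*

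**What the plan says.** Protocol 6.3 states: "Randomization is stratified based on KCCQ-23 CSS score (Main Cohort [Cohort A], Cohort C and Cohort D) and GDF-15 concentrations", the latter for Cohorts A and C only, both taken from SV1. Protocol 4.1 gives the cut-point as "KCCQ-23 CSS: <45 or ≥45". Protocol 4.2 gives the reason for stratifying as balance on these two key parameters.

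SAP 5.2.3 builds the MMRM from baseline, time, treatment and the two interactions with time, and lets other terms be added. SAP 6.1.1.1 fixes those terms for the primary analysis: LVEF, log GDF-15 "concentrations from SV1 and baseline log NT-proBNP will be fitted in the model". SAP 6.2.3 carries this over to 6MWD ("6MWD will be summarized and analyzed across all timepoints, in a similar manner to the" primary analysis), and SAP 6.2.4 does the same for PROMIS Fatigue. Body weight (6.3.7), activity (6.3.8) and the biomarkers (6.3.12) use the same covariates in an MMRM or ANCOVA. The example code in Appendix 4 has one term for the endpoint's own baseline and none for KCCQ.

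For clinical outcomes, SAP 5.2.8 lists among the possible Cox covariates "baseline log NT-proBNP, baseline KCCQ-23 CSS", and the Cox code contains a KCCQ term. SAP 5.2.6 says: "The logistic regression model will include treatment as a fixed term in the model"; neither its list of possible additions nor its code contains KCCQ.

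For efficacy endpoints, SAP 3 says "baseline is defined as the last measurement on study day 1".

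**The concern.** A stratification factor is normally a term in the analysis model. Stratifying removes between-arm imbalance on that factor. A model that ignores the factor still counts its variance as noise, so the reported SE is larger than the true spread of the estimate. 6MWD and PROMIS Fatigue are secondary endpoints tested at one-sided 5% (SAP 5.1), so unneeded width in their intervals costs a little power. The SAP also treats like cases differently: the Cox and logistic models address the same composite heart failure outcome (SAP 6.3.14) but list different covariates, and no reason is given.

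A related point concerns the NT-proBNP covariate. If it is the Day 1 value only, a missed Day 1 sample removes the participant from any model that contains it, including the primary one.

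**Working it through.** **1. Which models contain CSS**

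| Model | Baseline term | KCCQ-23 CSS named? |
|---|---|---|
| Primary MMRM (6.1.1.1) | CSS | Yes, as baseline |
| 6MWD, PROMIS Fatigue MMRM (6.2.3, 6.2.4) | own endpoint | No |
| Body weight, NT-proBNP MMRM (6.3.7, 6.3.12) | own endpoint | No |
| Activity, hsCRP, albumin, pre-albumin ANCOVA (6.3.8, 6.3.12) | own endpoint | No |
| Composite HF logistic (5.2.6, 6.3.14.1) | none | No |
| Composite HF Cox (5.2.8, 6.3.14.2) | none | Yes |

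SAP 4.3 says that a corrected stratum will be used in relevant analyses, but no model in Section 5.2 or Appendix 4 has a stratum term.

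**2. The plan's own figure.** Protocol 9.5 gives 190 randomised per arm and 15% discontinuation: 190 × 0.85 = 161.5, against about 161 stated. This reproduces and gives 322 completers. The documents show no SD, effect size or power for 6MWD or PROMIS Fatigue.

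**3. Size in a linear model.** Let r be the partial correlation of CSS with the outcome, given the terms already in the model. It is not in the documents, so a range is assumed. The SE without CSS exceeds the SE with continuous CSS by 1/√(1 − r²) − 1. As an illustration, the last column shows the power of a test that has 80% without CSS (one-sided 5%, normal approximation).

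| r (assumed) | Excess SE | 80% power becomes |
|---|---|---|
| 0 | 0% | 80.0% |
| 0.1 | 0.5% | 80.3% |
| 0.2 | 2.1% | 81.4% |
| 0.3 | 4.8% | 83.2% |

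**4. Splitting the excess.** A simulation used 322 participants, blocks of 4 within stratum, 30% below the cut-point (block size and share assumed), one time point and 6,000 runs per r. Mean model SEs:

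| r | No CSS | Stratum | Continuous CSS |
|---|---|---|---|
| 0.1 | 0.1115 | 0.1111 | 0.1110 |
| 0.2 | 0.1115 | 0.1102 | 0.1093 |
| 0.3 | 0.1115 | 0.1086 | 0.1065 |

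At r = 0.3 the stratum term accounts for 0.1115/0.1086 = 1.027, and going on to continuous CSS for 0.1086/0.1065 = 1.020. These are different gains. The actual spread of the estimates was 0.1093 without CSS, 0.1092 with the stratum and 0.1073 with continuous CSS. The stratum term therefore only corrects an overstated SE; continuous CSS also makes the estimate more precise. One-sided type I error without CSS was 0.047, with a simulation error of √(0.05 × 0.95/6,000) = 0.003. That is at or slightly below nominal.

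**5. Logistic model.** The formula in step 3 does not apply. With 380 participants, 10% to 20% events and a covariate log odds ratio of 0.3 to 0.8 per SD (all assumed), adding the covariate raised the mean SE of the treatment log odds ratio by 0.7% to 5.3% in simulation. The conditional odds ratio being estimated also changes.

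**6. NT-proBNP.** If 1% to 3% of Day 1 values are missing (assumed), 380 × 0.01 to 0.03 = 4 to 11 participants would leave the primary MMRM, because the SAS procedure in Appendix 4 drops records with a missing covariate. Protocol Table 1 schedules NT-proBNP at SV1, and inclusion criterion 2c requires that value in Cohorts A, C and D. In the responder code of Appendix 4, log NT-proBNP is among the imputation variables, so the same person could be kept there and lost from the primary MMRM.

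**The case against.** The SAP does not forbid the term. The MMRM, ANCOVA and logistic sections all use open lists of possible additions, and Appendix 4 is only a guide. The Cox list is equally permissive, and the Cox model has no own-baseline term, so naming CSS there is not a strict contradiction of the MMRM and ANCOVA sections. This stands in part: the term is allowed but not planned, and for two tested endpoints it is better fixed in advance. The logistic and Cox models are the like-for-like mismatch, and they concern tertiary outcomes.

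A reader might infer that these endpoints are analysed with clearly inflated SEs, or that the tests are invalid. The documents support neither. The size depends on a correlation that they do not give, zero is possible, and the direction is conservative. Nor can one say that adding CSS would shrink the SE in every model: step 5 shows the reverse for the logistic model.

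On NT-proBNP, the Day 1 rule is written for endpoints, the SAP does not say how a missing covariate is handled, and the missing rate is unknown. An SV1 value may also be up to 56 days old. These points limit the weight of that item but do not remove it.

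**Conclusion.** The point holds as a minor one. The linear models for endpoints outside the KCCQ do not plan for a factor used to stratify randomisation, although the primary model covers it and the Cox model names it. Their SEs are likely to be about 0.5% to 5% larger than with continuous CSS, for an assumed partial correlation of 0.1 to 0.3, and no larger if CSS adds nothing beyond the existing covariates. The simulation behind the split in step 4 is a single-visit simplification of the MMRM. Treatment estimates are not biased and type I error is not inflated. The NT-proBNP item is a smaller safeguard, worth perhaps 4 to 11 of 380 participants under an assumed 1% to 3% missing rate.

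**What to change.** Add continuous SV1 KCCQ-23 CSS as a covariate to the MMRM and ANCOVA models for every endpoint whose own baseline is not a KCCQ score. SV1 is the better choice than Day 1: it is the value used for stratification and is required for eligibility in Cohorts A, C and D, so adding it does not create a new way to lose participants. The continuous score is preferable to the stratum because only it improves precision. Add it to the non-imputed composite HF logistic model as well, for consistency with the Cox model and with no claim of a smaller SE.

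Separately, define the log NT-proBNP covariate as the last value on or before Day 1, before dosing. SV1 is then used when Day 1 is missing. The small downside is the possible age of that value.

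The cost is one covariate and one definition in the SAP, with matching edits to the example code. No new data are needed.

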#### 6.2.4. Change from baseline in PROMIS Fatigue 7a at Week 22 (Cohorts A and C)

Summaries and analyses will use efficacy approaches 1 and 3, as described in Section 5.2.

PROMIS Fatigue 7a will be summarized and analyzed across all timepoints, in a similar manner to the main analysis of the primary endpoint, as outlined in Section 6.1.1.1. This analysis will estimate the treatment effect related to Estimand 5 (as described in Section 2.2.4). Note that for efficacy approach 3, cohort will be included as a term in the statistical model.

#### 6.2.5. Incidence of TEAEs, TSEAEs, abnormal laboratory results and vital signs (All Cohorts [A, B, C and D])

For analysis of adverse events (AEs), laboratory abnormalities and vital signs *the Main Cohort (Cohort A) and Cohort C will be reported combined*, with data from the same treatment group combined across cohorts; *the open-label, PK cohort (Cohort B) will be reported separately; Cohort D will be reported separately*. The safety analyses will use the corresponding safety analysis sets, defined in Section 4.

##### 6.2.5.1. Adverse Events

Adverse events (Tier 1, 2 and 3 AEs as described in Section 3.2.5.1) will be summarized by treatment group (including ponesegromab combined) and overall, in accordance with sponsor reporting standards. The adverse events will be sorted in descending frequency within a system organ class. If applicable, subject discontinuations due to adverse events will be detailed and summarized.

Incidence and severity of TEAE and TSEAE tables will additionally be produced ('All causality' and 'Treatment related', separately) to summarise the total number of adverse events by preferred term, which will be reported by treatment group (including ponesegromab combined) and overall.

TEAEs classed as Tier 2 events (except for the PK cohort) will each be tabulated by treatment group (including ponesegromab combined). The number and percentage of participants will be presented, along with the risk difference (and 95% confidence interval) between each dose of ponesegromab and placebo. No adjustment for multiplicity will be used.

Tier 2 TEAEs (except for the PK cohort) will also be presented graphically in two-panel plots; the left panel will present the proportions of TEAEs observed in a dose group of ponesegromab (including ponesegromab combined) and separately placebo, while the right panel will display the 95% confidence interval for the risk differences for each TEAE. A vertical line corresponding to the value of 0 will be added to the right-hand plot. Each panel will be paged by treatment group of ponesegromab.

Tier 2 TEAE outputs will be ordered in descending point estimate of risk difference within System Organ Class. If two or more events have the same frequency they will be sorted alphabetically by preferred term. Footnotes will be included on the tables to provide proper interpretation of confidence intervals and to describe how the comparison was conducted, e.g. "Confidence intervals are not adjusted for multiplicity and should be used for screening purposes only. 95% Confidence intervals are provided to help gauge the precision of the estimates for Risk Difference. Risk Difference is computed as ponesegromab versus placebo."

It should be recognized that most studies are not designed to reliably demonstrate a causal relationship between the use of a pharmaceutical product and an adverse event or a group of adverse events. Except for select events in unique situations, studies do not employ formal adjudication procedures for the purpose of event classification. As such, safety analysis is generally considered as an exploratory analysis and its purpose is to generate hypotheses for further investigation. The 3-tier approach facilitates this exploratory analysis.

TEAE classed as Tier 1 events (except for the PK cohort) will be tabulated by treatment group. The number and percentage of participants, reporting events listed in the pre-specified Tier 1 list, will be tabulated by treatment group (with ponesegromab treatment groups combined only) and overall, and by severity. Note that Tier 1 events are not planned to be presented graphically due to the small number of expected events.

Note that Tier 1 and 2 events will not be presented for the open-label, PK cohort (Cohort B).

Injection site reactions (ISR) will also be summarized by treatment group (including ponesegromab combined) and overall, in accordance with sponsor reporting standards. The ISRs will be sorted in descending frequency within a system organ class. Incidence and severity of ISR tables will additionally be produced ('All causality' and 'Treatment related', separately) to summarise the total number of ISR by preferred term, which will be reported by treatment group (including ponesegromab combined) and overall.

Potential immunogenic AEs will be summarized by medical evaluation category (see Section 3.2.5.1) and treatment groups (including ponesegromab combined) and overall.

